## 10.2 Sample size and power considerations

Data from previous PK studies of the test product, 1897 and 162020 (§ 1.4.1and 1.4.2) were used to calculate the sample size of the present study, as shown in the table below.

Table 10.2.1 Sample size calculation

Parameter	δ	CV WR	α	β	n	N=2n
$C_{max}$	1.11	0.3266	0.1	0.2	26	52
$AUC_{0-t}$	1.0917	0.1265	0.1	0.2	4	9

 $\delta$ : ratio of geometric means of the considered parameter;  $CV_{WR}\%$ : within-subject variability;  $\alpha$ : type 1 error;  $\beta$ : type 2 error; n: number of subjects per sequence; N: total sample size

Variability of AUC0-t and Cmax (CVWR) actually observed in study 162020 (§ 1.4.2) was used in the calculation. The actual ratio of geometric means of AUC0-t of study 162020 was 1.0917,

whilst that of  $C_{max}$  observed in study 162020 was 1.1582. This high ratio did not prevent the demonstration of bioequivalence of the formulations in study 162020 also for  $C_{max}$ . However, the calculation of the sample size for the present study using a  $\delta$  of 1.1582 would be 126 subjects. Considering that the enrolment of at least 126 subjects in a bioequivalence study would be hardly justifiable, that bioequivalence between the test IMP and Rilutek 50 mg tablets available in US was demonstrated in study 162020 in 30 subjects, who completed the study, and that the actual  $\delta$  of  $C_{max}$  obtained in the previous pilot study 1897 was 0.9436, which is notably nearer the equality, i.e. ratio = 1.00, than the ratio 1.1582 observed later in study 162020, a ratio of 1.11 was postulated in the present sample size calculation. Indeed, maintaining  $CV_{WR}$ ,  $\alpha$  and  $\beta$  unchanged and assuming as  $C_{max}$  ratios, alternately, 1.05 and 1.10, sample sizes of 26 and 46 subjects, respectively, would be necessary to demonstrate bioequivalence in terms of  $C_{max}$ .

Taking into account this premise, when the sample size in each sequence group is 26 (and the total sample size is 52), a replicate crossover design will have 80% power to reject both the null hypothesis that the ratio of the test mean to the reference mean of  $C_{\text{max}}$  is below 0.800 and the null hypothesis that the ratio of test mean to the reference mean of  $C_{\text{max}}$  is above 1.250 (i.e. that the test and standard are not equivalent, in favour of the alternative hypothesis that the means of the two treatments are equivalent) assuming that data will be analysed in the natural log scale using t-tests for differences in means and that each t-test will be made at the 5.0% significance level.

In conclusion, 54 subjects will be enrolled in order to have 52 completed subjects.

#### 10.3 Demographic, baseline and background characteristics

Critical demographic characteristics will be examined according to qualitative or quantitative data. Qualitative data will be summarised in contingency tables. Quantitative data will be summarised using classic descriptive statistics.

# 10.4 Drug administration and analysis of film dissolution

The date and time of film placement, of film dissolution, of accidental film swallowing and reference tablet administrations will be listed. Dosing time is defined as the time the film is placed on the subject's tongue.

The actual time of film dissolution will be summarised by descriptive statistics.

The dose per body weight of riluzole will be listed and summarised by descriptive statistics. The body weight collected at the screening visit will be used for the calculation.

The minimum and maximum number of days of wash-out between periods will be presented.

## 10.5 Test IMP palatability

Test IMP palatability scores will be listed and summarised in tables of frequency.

## 10.6 Analysis of pharmacokinetic parameters

## 10.6.1 Descriptive pharmacokinetics

A descriptive PK will be presented. The results will be displayed and summarised in tables and figures. Individual and mean curves (+SD at sampling times), indicating inter-subject variability, will be plotted. Data below the lower quantification limit (BLQL) will be considered as 0 in the calculations and presented as BLQL in listings and tables. As a consequence of BLQL (i.e. 0) values, calculated geometric means (if requested) could be null. For this reason, in the presence of any null value, the geometric mean will be reported as not calculated (NC).

### 10.6.2 Statistical comparison of pharmacokinetic parameters

According to the current European Guideline (9), plasma riluzole  $AUC_{0-t}$ ,  $AUC_{0-\infty}$  and  $C_{max}$  will be analysed using analysis of variance (ANOVA). A mixed linear model will be used to make statistical inferences about the values of  $C_{max}$  and  $AUC_{0-t}$ . In order to correctly assume normality and homoscedasticity, the data will be transformed prior to analysis using a neperian logarithmic transformation in compliance with the EMA guideline.

The 90% CI of the ratio of the population means (test/reference), for the parameters under consideration will be calculated. This method is equivalent to the corresponding two one-sided test procedure with the null hypothesis of bioequivalence at the 5% significance level.

- ➤ The statistical analysis will take into account treatment, period, sequence and subject within sequence as fixed effects.
- Acceptance criterion for bioequivalence in terms of extent of absorption (AUC0-t as primary variable and AUC0- $\infty$  as secondary variable) will be that the 90% CI of this ratio has to lie within the range 80.00-125.00%.
- Due to the replicate design of the study, if the within-subject variability ( $CV_{WR}\%$ ) of  $C_{max}$  of plasma riluzole after administration of the reference formulation is >30%, the reference-scaled BE approach will be used. Bioequivalence acceptance range for  $C_{max}$  will be widened, in compliance with the guideline, as exemplified in Table 10.6.2.1.
- $ightharpoonup CV_{WR}\%$  will be calculated by applying the formula  $CV_{WR}(\%) = 100\sqrt{e^{S^2_{WR}}-1}$ , where  $S^2_{WR}$  is the within-subject variation plasma riluzole after administration of the reference formulation only.
- The extent of the widening will be defined on the basis of the within-subject variability actually observed in the study according to [U, L] = exp [±k·sWR], where U is the upper limit of the acceptance range, L is the lower limit of the acceptance range, k is the regulatory constant set to 0.760 and SwR is the within-subject standard deviation of the log-transformed values of Cmax of plasma riluzole after administration of the reference formulation.

Moreover, the widening of the acceptance range for Cmax is justified considering the favourable safety and tolerability profile of riluzole as demonstrated for the formulations authorised on the market.

Table 10.6.2.1 Examples of widened bioequivalence acceptance limits of  $C_{max}$  according to its actual  $CV_{WR}$ 

CV WR %*	Lower Limit	Upper Limit
30	80.00	125.00
35	77.23	129.48
40	74.62	134.02
45	72.15	138.59
≥50	69.84	143.19

\*:  $CVWR(\%) = 100\sqrt{e^{S^2WR} - 1}$ ; source: reference (9)

tmax and t1/2will be compared between treatments by the non-parametric Friedman test.

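### Protocol 10.6.2 and SAP 8.6.3 reverse the null hypothesis and attach an unqualified 5% level to Cmax, whose limits are estimated from the same data; at the planning CVwR the error at the limit is about 6.9%

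*Protocol*

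**What the plan says.** Protocol 10.6.2 names AUC0-t, AUC0-∞ and Cmax as the parameters to be analysed and then states: "The 90% CI of the ratio of the population means (test/reference), for the parameters under consideration will be calculated". The next sentence is "This method is equivalent to the corresponding two one-sided test procedure with the null hypothesis of bioequivalence at the 5% significance level". No exception is made for Cmax. SAP 8.6.3 repeats both sentences.

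The bullets that follow fix the AUC limits at 80.00-125.00%. For Cmax they widen the limits when the reference CVwR found in the study is above 30%. The widened limits are exp(±0.760·sWR), and "The extent of the widening will be defined on the basis of the within-subject variability actually observed in the study". Protocol 4.2 and Table 10.6.2.1 stop the widening at 69.84-143.19%, reached at a CVwR of 50%.

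Protocol 10.2 and SAP 8.3 describe the tests the other way round. The hypotheses to be rejected are a ratio below 0.800 and a ratio above 1.250, that is "that the test and standard are not equivalent, in favour of the alternative hypothesis that the means of the two treatments are equivalent", and "each t-test will be made at the 5.0% significance level".

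**The concern.** The two descriptions of the null cannot both be right. A test whose null is bioequivalence would need evidence to reject equivalence; the planned procedure needs evidence to conclude it.

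The second problem is the level. Requiring a 90% interval to lie inside two limits is the same as two one-sided 5% tests when those limits are constants. For Cmax they are not: the data decide whether the limits are widened, and by how much. The interval allows for sampling error in the ratio but not in the limits, so the stated 5% is not a property of the Cmax rule.

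Cmax is a primary variable and determines the sample size. The earlier studies put its CVwR at 32.13% and 32.66%, just above the 30% switch. As the text stands, a reader of the report would take a Cmax claim made under widened limits as a 5%-level result.

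**Working it through.** **Inputs from the documents.** 52 completers, sequences RTRT and TRTR (Protocol 10.2, 4.2); planning CVwR of Cmax 32.66% (Table 10.2.1); switch at 30% and constant 0.760 (10.6.2); cap at CVwR 50% (Table 10.6.2.1); treatment, period, sequence and subject within sequence as fixed effects (10.6.2). The residual degrees of freedom are 3×52−4 = 152, and those for sWR from reference data alone are 52−2 = 50.

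**Assumptions, not in the documents.** CVwT = CVwR; no subject-by-formulation variance; the Cmax error is evaluated at the limit implied by the true CVwR. The documents state no point-estimate constraint for Cmax, so none is applied.

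**Step 1: the plan's own figure.** With limits fixed at 80.00-125.00 and a true ratio of 1.25, simulation of the planned analysis gives 5.0% at a CV of 32.66% and 5.0% at 12.65%, the AUC0-t value. The stated level reproduces for fixed limits.

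**Step 2: the Cmax limit at the planning value.** s²wR = ln(1 + 0.3266²) = 0.1014, so sWR = 0.3184. The log limit is 0.760 × 0.3184 = 0.2420, a ratio of 1.274.

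**Step 3: a hand check of the size.** The standard error of the log ratio is √(0.1014/52) = 0.0441. With t = 1.655 on 152 df the interval's half-width is about 0.0731. The estimated log limit has its own standard error, roughly 0.760 × 0.3184/√(2×50) = 0.0242, which the interval ignores. Combining the two gives √(0.0441² + 0.0242²) = 0.0503, and 0.0731/0.0503 = 1.45, a one-sided tail of about 7.3%. This ignores the floor at 1.25, the cap, and the fact that sWR also enters the interval's width.

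**Step 4: simulation of the full rule.** Draw the log ratio around the log limit with variance 0.1014/52. Draw s²wR from a chi-square on 50 df and include it in the 152-df residual. Apply the switch, constant and cap, and count the intervals that lie inside the limits. The error is 6.9%, with the limits widened in about 76.5% of trials. A subject-level least-squares simulation also gave 6.9%.

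**Step 5: range over the true CVwR**, same assumptions:

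| True CVwR | True limit (ratio) | Error at the limit |
|---|---|---|
| 20% | 1.250 | 5.0% |
| 25% | 1.250 | 5.1% |
| 28% | 1.250 | 6.0% |
| 30% | 1.250 | 8.2% |
| 32.66% | 1.274 | 6.9% |
| 35% | 1.295 | 6.7% |
| 40% | 1.340 | 6.6% |
| 45% | 1.386 | 5.6% |
| 50% | 1.432 | 3.4% |

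The peak is at the switch: with a true CVwR of 30% no widening is due, yet about 47% of trials widen. At the cap the estimated limits can only be too narrow, so the error falls below 5%.

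**Step 6: sensitivity at 32.66%.** CVwT from 40% down to 20% gives 6.6% to 7.5%. A point-estimate constraint of 80-125% leaves 6.9%.

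**The case against.** The strongest reply is that the sentence only describes the interval, comes before the widening bullets, and uses 5% as a conventional nominal level. The widening rule is pre-specified and attributed to the cited guideline, the null is stated correctly elsewhere, and no decision would change. Much of this stands: the rule is not at fault and the reversed null is a slip of wording. But nominal is what the text ought to say and does not. It covers all the parameters, Cmax included, without qualification.

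It is also fair that the error figure depends on where the null is placed. The documents define the widened limits only through the observed variability, so the limit implied by the true CVwR is a reviewer's definition. If a true ratio of 1.25 is counted as non-equivalent at a CVwR of 32.66%, the rule passes it 13.7% of the time. Any reported figure must therefore state its definition.

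Three stronger readings are tempting, and the documents support none of them:

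- **That this trial's error is 8.2%.** That is the highest value in the table, at a CVwR of 30%. The earlier studies observed 32.13% and 32.66%.
- **That AUC also exceeds 5%.** This would need appreciable subject-by-formulation variance. In Table 1.4.2.1 the 90% CI for AUC0-t is 105.67-112.79%. Taking 30 balanced completers and t = 1.701 on 28 df, SE = ln(112.79/105.67)/(2×1.701) = 0.0192, so 30×SE² = 0.011. That is below s²wR = ln(1 + 0.1265²) = 0.0159, so with CVwT = CVwR the implied subject-by-formulation variance is negative. Even with no test variance at all, its SD would be at most about 0.06, or about 0.10 if the interval came from a fixed-effects model.
- **That the unclear model causes the Cmax excess.** The text says "A mixed linear model will be used to make statistical inferences about the values of" Cmax and AUC0-t, and then "The statistical analysis will take into account treatment, period, sequence and subject within sequence as fixed effects". That ambiguity is real but separate. A model with a random subject-by-formulation effect gives 7.3% at 32.66%, against 6.9% with all effects fixed.

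**Conclusion.** Wrong as written, in both documents. The null is reversed, which needs no calculation to show. The 5% level is correct for limits fixed at 80.00-125.00 under the model's assumptions and incorrect as a statement about Cmax under the widening rule. At the planning CVwR the error at the limit is about 6.9%, or 6.9/5 = 1.4 times the stated level. Over CVwR from 20% to 50% it ranges from 3.4% to 8.2%. These figures rest on 52 subjects, the fixed-effects ANOVA, CVwT = CVwR, no subject-by-formulation variance, no point-estimate constraint, and a true ratio at the limit implied by the true CVwR. They are not errors at the ratios discussed in Protocol 10.2 (0.9436, 1.11, 1.1582), all of which lie inside 0.80-1.25.

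A reader might infer that the widening rule is invalid or that the trial is the wrong size. Neither follows: what fails is a stated property of the rule, and no decision criterion changes.

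**What to change.** In Protocol 10.6.2 and SAP 8.6.3:

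1. Name the null as non-equivalence, in line with Protocol 10.2 and SAP 8.3.
2. State that 5% is the level of each one-sided test against limits fixed at 80.00-125.00, and is only nominal for Cmax under the widening rule.
3. Report the simulated Cmax error at the planning CVwR together with its range over CVwR. List the assumptions: number of subjects, CVwT, subject-by-formulation variance, where the true ratio is placed, any point-estimate constraint, and the analysis model used.

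Keep the 90% interval, the widening rule and the sample size unchanged. The cost is a wording change in two sections and one short simulation statement, with no new data. The downside is that the stated Cmax error rate becomes less favourable.

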#### Data analysis:

The data documented in this trial and the measured clinical parameters will be described using classic descriptive statistics for quantitative variables and frequencies for qualitative variables. The statistical analysis will be performed using SAS® version 9.3 (TS1M1) or higher (the actual versions will be stated in the final report). The statistical analysis of pharmacokinetic parameters will be performed using Phoenix WinNonlin® version 6.3 or higher and SAS® version 9.3 (TS1M1) or higher. Cmax and AUC0-t will be compared using analysis of variance (ANOVA) for a 2-sequence, 4-period replicate cross-over design on log-transformed data. Acceptance criterion

or higher and SAS version 9.3 (TS1M1) or higher.  $C_{max}$  and  $AUC_{0-t}$  will be compared using analysis of variance (ANOVA) for a 2-sequence, 4-period replicate cross-over design on log-transformed data. Acceptance criterion for bioequivalence is that the 90% confidence interval for the test/reference ratio of the  $AUC_{0-t}$  geometric means is within the 80.00-125.00 range, according to the current EMA guideline for bioequivalence investigations. Due to the replicate design of the study, if the within-subject variability of  $C_{max}$  of plasma riluzole after administration of the reference treatment is >30%, bioequivalence range for  $C_{max}$  will be widened. The extent of widening will be determined on the basis of the actual within-subject variability observed in study  $C_{max}$ .

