The ANOVA performed on the primary riluzole PK parameters clearly demonstrated the bioequivalence of the novel riluzole orodispersible film to Rilutek  $^{\circledR}$  50 mg tablets available in US.  $CV_{WR}$  of plasma riluzole  $AUC_{0-t}$  and  $AUC_{0-\infty}$  was less than 30% and since their 90% geometric confidence interval (CI) were respectively 105.67% to 112.79% and 105.58% to 112.61% both falling within the acceptance range of 80.00% to 125.00%, test and reference formulations were bioequivalent in terms of extent of exposure to riluzole.

Since  $CV_{WR}$  of  $C_{max}$  was higher than 30%, a scaled average bioequivalence approach was used according to the FDA guidance on bioequivalence studies. Therefore, also in terms of rate of absorption of plasma riluzole, the hypothesis of bioequivalence of test and reference formulation was accepted, because the 95% upper confidence bound was  $\leq 0$  and the geometric mean ratio was within the interval 80.00% to 125.00%.

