## 4.2 Discussion of design

The study was designed in agreement with the EMA guideline "Guidance on the investigation of bioequivalence", CPMP/EWP/QWP/1401/98 Rev. 1 January 2010 (9). The well-known high variability of riluzole led to the choice of the replicate cross-over design as suggested by the current EMA guideline. According to the guideline, an enlargement of the acceptance interval for bioequivalence in terms of  $C_{max}$  is allowed up to 69.84-143.19% in relation to the actual intra-subject variability of riluzole  $C_{max}$  found in this study with the reference treatment, by keeping in consideration the favourable safety profile of the test formulation previously observed in 3 clinical studies. In detail, a  $C_{max}$  within-subject variability >30% was found in the previous pilot study and =32.66% in the previous bioequivalence study performed in USA (§ 1.4.2). According to the 2-arm cross-over study design, each randomised subject will be allocated to one of 2 sequences of IMP administrations in the 4 study periods according to a computer generated randomisation list (see § 8.1). Balance between the sequences will be made so that subjects have the same chances to be assigned to either sequence (either RTRT or TRTR in the 4 consecutive periods).

An open-label design will be used since the primary end-point of the study is based on objective measurements of riluzole in plasma and the outcome variables could not be influenced by the subjects or investigator being aware of the administered products. The bioanalysis will be performed under blinded conditions.

The washout period of 7 days was estimated to be adequate. Based upon a half-life of 12 h (Rilutek SmPC reference: 7), it is anticipated that minimal plasma levels would be achieved in 5 days thus allowing dosing every 7 days. Blood sampling time-points were selected on the basis of the known PK profile of riluzole and on the basis of previous Phase I studies of the same test formulation administered to healthy volunteers.

The dose for the present study was selected based on EMA Rilutek® European Public Assessment Report (EPAR) (10), which recommends a dose regimen of 50 mg (one film-coated tablet) twice a day in the common clinical practice. The dose of 50 mg is the minimal unit dose.

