8.6.3 Statistical comparison of pharmacokinetic parameters

According to the current European Guideline on the Investigation of Bioequivalence (3), plasma riluzole AUC_{0-t} , $AUC_{0-\infty}$ and C_{max} will be analysed using analysis of variance (ANOVA) (Table 14.2.3.1).

A mixed linear model will be used to make statistical inferences about the values of C_{max} and AUC_{0-t}. In order to correctly assume normality and homoscedasticity, the data will be transformed prior to analysis using a neperian logarithmic transformation in compliance with the EMA guideline.

The 90% CI of the ratio of the population means (test/reference), for the parameters under consideration will be calculated. This method is equivalent to the corresponding two one-sided test procedure with the null hypothesis of bioequivalence at the 5% significance level.

- The statistical analysis will take into account treatment, period, sequence and subject within sequence as fixed effects.
- Acceptance criterion for bioequivalence in terms of extent of absorption (AUC_{0-t} as primary variable and AUC_{0-∞} as secondary variable) will be that the 90% CI of this ratio has to lie within the range 80.00-125.00%.
- Due to the replicate design of the study, if the within-subject variability (CV_{WR} %) of C_{max} of plasma riluzole after administration of the reference formulation is >30%, the reference-scaled BE approach will be used. Bioequivalence acceptance range for C_{max} will be widened, in compliance with the guideline, as exemplified in Table 8.9.3.1.
- $CV_{WR}\%$ will be calculated by applying the formula $CV_{WR}(\%) = 100\sqrt{e^{S^2_{WR}} 1}$, where S^2_{WR} is the within-subject variation plasma riluzole after administration of the reference formulation only.
- The extent of the widening will be defined on the basis of the within-subject variability actually observed in the study according to $[U, L] = \exp [\pm k \cdot S_{WR}]$, where U is the upper limit of the acceptance range, L is the lower limit of the acceptance range, k is the regulatory constant set to 0.760 and S_{WR} is the within-subject standard deviation of the log-transformed values of C_{max} of plasma riluzole after administration of the reference formulation.

CV _{WR} %*	Lower Limit	Upper Limit
30	80.00	125.00
35	77.23	129.48
40	74.62	134.02
45	72.15	138.59
≥50	69.84	143.19

Table 8.9.3.1 Examples of widened bioequivalence acceptance limits of C_{max} according to its actual CV_{WR}

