*: $CVWR(\%) = 100\sqrt{e^{S^2_{WR}} - 1}$; source: reference (3)

The value of within-subject variability of C_{max} (after administration of the reference formulation), obtained using the formula above, will be reported in the table 14.2.3.2.

 t_{max} and $t_{1/2}$ will be compared between treatments by the non-parametric Friedman test (Table 14.2.3.3).

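### Does the widened Cmax rule need a written condition on the test/reference ratio itself?

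*Protocol*

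**What the plan says.** Protocol 10.6.2 sets the trigger: if the reference CVWR of Cmax "is >30%, the reference-scaled BE approach will be used". The range then "will be widened, in compliance with the guideline, as exemplified in Table 10.6.2.1". SAP 8.6.3 has the same sentence, pointing to its own table: "will be widened, in compliance with the guideline, as exemplified in Table 8.9.3.1". Both sections give the limits as exp(±0.760·sWR) and add: "The extent of the widening will be defined on the basis of the within-subject variability actually observed in the study". The synopsis agrees: "The extent of widening will be determined on the basis of the actual within-subject variability observed in study". Protocol 4.2 supplies the cap: widening "is allowed up to 69.84-143.19% in relation to the actual intra-subject variability of riluzole" Cmax.

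The one sentence in 10.6.2 and 8.6.3 that imposes 80.00-125.00% is a confidence-interval criterion for AUC. A condition on the Cmax ratio appears only in Protocol 1.4.2, in the account of the earlier US study, where "a scaled average bioequivalence approach was used according to the FDA guidance on bioequivalence studies". That is a different procedure from the one planned here.

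For reporting, SAP 8.6.3 says the reference variability of Cmax, "obtained using the formula above, will be reported in the table 14.2.3.2". The shell of Table 14.2.3.1 shows the Cmax point estimate with both 90% confidence limits. The shell of Table 14.2.3.2 shows S²WR and CVWR.

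**The concern.** Widening the range moves the confidence limits outward, so at high enough variability a product whose estimated ratio lies above 1.25 (or below 0.80) could still pass. A separate condition on the ratio would block that. The plan spells out every other element of the rule and is silent on this one. Its only mention of such a condition belongs to another study under another method, so a reader cannot tell whether it carries over.

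If the observed variability fell in the region where this matters, the same data could pass or fail on Cmax according to how the analyst read the silence. In an open-label study with Cmax as a primary variable, that should be settled before results are seen.

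**Working it through.** **Inputs.** From the documents: k = 0.760, cap 69.84-143.19%, trigger CVWR > 30%, 90% CI (Protocol 4.2 and 10.6.2; SAP 8.6.3); planning CVWR 32.66%, assumed ratio 1.11, earlier observed ratio 1.1582, 52 completers (Protocol 10.2); sequences RTRT and TRTR. Assumed, because the documents do not give it: test and reference have the same within-subject SD (sWT = sWR), no subject-by-formulation interaction, balanced sequences, no missing periods.

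**1. Reproduce the plan's limits.** sWR = √ln(1 + CVWR²); limits = exp(±0.760·sWR). At CVWR 35%, sWR = 0.3399 and 0.760 × 0.3399 = 0.2584, giving 77.23-129.48%. All five rows of Table 10.6.2.1 reproduce to two decimals. At 32.66%, sWR = 0.3184 and the limits are 78.51-127.37%.

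**2. Largest ratio that can pass.** The model has fixed effects for treatment, period, sequence and subject within sequence. Residual df with 52 × 4 = 208 observations are 208 − 1 − 1 − 3 − 1 − 50 = 152, so t(0.95) = 1.655. The half-width of the 90% CI on the log scale is 1.655·sW/√52. The largest passing ratio is exp(log upper limit − half-width).

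| Observed CVWR | Log upper limit | Half-width | Largest passing ratio |
|---|---|---|---|
| 32.66% | 0.2420 | 0.0731 | 1.184 |
| 40% | 0.2928 | 0.0884 | 1.227 |
| 44% | 0.3197 | 0.0965 | 1.250 |
| 45% | 0.3264 | 0.0986 | 1.256 |
| 50% | 0.3590 (cap) | 0.1084 | 1.285 |
| 60% | 0.3590 (cap) | 0.1273 | 1.261 |
| 65% | 0.3590 (cap) | 0.1362 | 1.2495 |

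With equal observed SDs the condition can bind only between about 44% and 65%. Those are not fixed bounds. The interval uses a residual variance pooled over both products, while the widening uses the reference alone. If sWT/sWR were 0.5 the affected range would be about 40-87%; at 1.25, about 47-56%; at 1.5 the condition never binds.

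**3. How likely such variability is.** With 50 df for the reference variance, P(observed CVWR > 44%) = P(χ²₅₀ > 50 × 0.4207²/0.3184²) = P(χ²₅₀ > 87.3) = 0.09% at a true CVWR of 32.66%. It is 16.6% at a true 40% and 55.5% at 45%.

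**4. Effect on the verdict.** Simulated trials, N = 52, several million per case, Cmax pass rate without and with an 80.00-125.00% condition on the ratio:

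| True CVWR | True ratio | Without | With | Trials changed |
|---|---|---|---|---|
| 32.66% | 1.11 | 92.0% | 92.0% | 0.001% |
| 32.66% | 1.158 | 69.3% | 69.2% | 0.008% |
| 40% | 1.158 | 82.7% | 82.1% | 0.7% |
| 45% | 1.158 | 88.2% | 85.8% | 2.4% |
| 50% | 1.158 | 90.3% | 86.3% | 4.0% |
| 60% | 1.158 | 86.1% | 83.6% | 2.4% |

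At 32.66% the share changed stays at or below 0.05% for true ratios up to 1.30. The few affected trials at 32.66% and 1.158 mostly (about two thirds) have an observed CVWR below 44%. They arise because the observed test and reference variances differ by chance, which confirms that the 44-65% band is not sharp.

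**The case for a change.** The best argument for a change is that it costs one sentence and closes an ambiguity in a primary decision rule. The text is indeed silent. Because 10.6.2 and 8.6.3 restate the trigger, constant and formula, leaving this one element to a citation is uneven drafting. The variability is also uncertain: assuming 28 df from the earlier study's 30 completers, the upper 95% limit for its 32.66% is √(28 × 0.3184²/χ²₀.₀₂₅,₂₈), which converts to a CVWR of about 45%. The plan's own table runs to 50% and beyond, and the earlier study's ratio was 1.1582. In that corner the condition would decide a few trials in a hundred.

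What stands is that the condition is unwritten and that a sponsor may reasonably add a line. What does not stand is that the plan is wrong without it. The documents do not reproduce the guideline, so they cannot show that 80.00-125.00% is the missing text. They do bind the analyst to the guideline for the widening. SAP section 1 also ties the methods to the guideline and to its questions-and-answers document. An analyst who reaches the widening step must consult that source and apply what it says. Nor do the outputs hide anything: the ratio, its interval and S²WR are all tabulated, so any reader can compute the applied limits and check the ratio.

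**Conclusion.** No change is called for. This is a detail left to a cited source that the plan instructs the analyst to follow, not a faulty or contradictory rule. At the documented variability (32.13% in the pilot study, 32.66% in the later one) the choice has practically no effect: under 0.01% of Cmax verdicts at true ratios of 1.11 to 1.158, with power near 92% either way. It would reach about 2.4 to 4.0 percentage points, at a true ratio of 1.158, only if the true CVWR were about 45-60%. Adding the applied limits to Table 14.2.3.2 would be a convenience.

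The sizes rest on 52 completers with full data, equal true within-subject variances and no subject-by-formulation interaction. The conclusion that no rule is wrong rests on the text alone, and in particular on the explicit tie between the widening and the guideline.
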